6.4 Maintenance Phase (84-day Cycles)

The Maintenance Phase will start 21 days after Day 1 of the previous treatment cycle. During the Maintenance Phase, subjects will receive tabelecleucel on Day 1 and pembrolizumab on Day 1, Day 21 (\pm 2), Day 42 (\pm 2), and Day 63 (\pm 2) followed by a response assessment at the observation visit on Day 77 (\pm 2) of each 84-day cycle until disease progression, unacceptable toxicity, or a total of 35 infusions of pembrolizumab (including for treatment, consolidation, and/or maintenance) have been given.

6.4.1 **Maintenance: Day 1**

- Physical examination including weight
- AEs
- Concomitant medications

- Hematology panel: CBC with platelet count and differential
- Full chemistry panel: sodium, potassium, chloride, total carbon dioxide, BUN, creatinine, glucose (fasting), total calcium, albumin, total protein, serum creatinine, TBIL, ALT, AST, alkaline phosphatase, and tests of thyroid function (TSH, T3, and T4)
- **CCI** [REDACTED]
- **Maintenance Cycle 1 only:** **CCI** [REDACTED]
[REDACTED]
[REDACTED]
- Investigational product infusions:
 - Pembrolizumab will be administered prior to tabelecleucel
 - Tabelecleucel will be administered 1 hour (\pm 10 minutes) after completion of the administration of pembrolizumab only if no infusion reactions related to pembrolizumab are observed/reported or in the case of such a reaction, the subject has recovered
- Vital signs (body temperature, BP, HR, and respiratory rates) at the following times:
 - immediately before the pembrolizumab infusion
 - within 10 minutes following the conclusion of the pembrolizumab infusion
 - immediately before the tabelecleucel infusion
 - within 10 minutes following the conclusion of the tabelecleucel infusion
 - 1 hour (\pm 10 minutes) after initiation of the tabelecleucel infusion
 - If the subject experiences symptoms/signs of an infusion reaction, follow-up may be longer, as clinically indicated.

6.4.2 Maintenance: Day 21, Day 42, and Day 63

- Physical examination including weight
- AEs
- Concomitant medications
- Hematology panel: CBC with platelet count and differential
- Abbreviated chemistry panel: serum creatinine, TBIL, ALT, AST, alkaline phosphatase, glucose (fasting) and tests of thyroid function (TSH, T3, and T4)
- **Maintenance Cycle 1 Day 21 only:** **CCI** [REDACTED]
[REDACTED]
[REDACTED]
- Investigational product infusion: pembrolizumab

- Vital signs (body temperature, BP, HR, and respiratory rates) at the following times:
 - immediately before the infusion
 - within 10 minutes following the conclusion of the infusion
 - 1 hour (\pm 10 minutes) after initiation of the infusion
 - If the subject experiences symptoms/signs of an infusion reaction, follow-up may be longer, as clinically indicated.

6.4.3 Maintenance: Day 77

- Radiographic assessments (including CT with contrast or MRI) as described in Section 7.1
- Concomitant medications
- AEs

6.5 End-of-Treatment Visit

An End-of-Treatment visit will be performed 30 ± 5 days after the last dose of investigational product (tabelecleucel and/or pembrolizumab) for all subjects, including those who discontinue early from treatment, consolidation, and/or maintenance. The following assessments/procedures will be performed:

- Physical examination including weight
- Concomitant medications
- AEs
- Vital signs (body temperature, BP, HR, and respiratory rate)
- Hematology: CBC with platelet count and differential
- Full chemistry panel: sodium, potassium, chloride, total carbon dioxide, BUN, creatinine, glucose (fasting), total calcium, albumin, total protein, serum creatinine, TBIL, ALT, AST, alkaline phosphatase, and tests of thyroid function (TSH, T3, and T4)
- CMV antibody (if negative at baseline)
- Pregnancy test for women of childbearing potential (serum)
- Performance status: ECOG for subjects > 16 years of age or Lansky score for subjects 12 to 16 years of age
- **CCI** [REDACTED]
[REDACTED]
- **CCI** [REDACTED]
- **Only if within 30 days from the last dose of tablecleucel:** **CCI** [REDACTED]
[REDACTED]
[REDACTED]

- Radiographic assessments (including CT with contrast or MRI) as described in Section 7.1

6.6 Quarterly Follow-up

Quarterly Follow-up will occur every 90 ± 14 days for 12 months after the last dose of investigational product (tabelecleucel and/or pembrolizumab) or until disease progression. The last Quarterly Follow-up Visit will be considered the end-of-study for the subject. The following assessments/procedures will be performed:

- Radiographic assessments including CT with contrast or MRI for subjects with CR, PR, or SD who did not complete maintenance cycles until 35 infusions of pembrolizumab was given or until disease progression - as described in Section 7.1
- Survival and disease status (ie, an investigator assessment based on clinical and radiographic assessments)
- For AEs reporting, refer to Section 8.5

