During the Maintenance Phase, subjects will receive tabelecleucel on Day 1 and pembrolizumab on Day 1, Day 21, Day 42, and Day 63 of 84-day maintenance cycles, which will continue until disease progression, unacceptable toxicity, or a total of 35 pembrolizumab infusions (including for treatment, consolidation, and maintenance) have been given. After completing an End-of-Treatment (EOT) Visit 30 days after the last dose of investigational product, subjects will enter quarterly follow-up until 12 months after the last dose of investigational product or until disease progression. During this last phase, survival and disease status will be collected through clinic visits or telephone contact. The end-of-study is defined as the date of the last quarterly follow-up.

Definitions

Subject replacement: Subjects who discontinue due to a DLT after receiving both pembrolizumab and tabelecleucel during the 21-day DLT assessment window will not be replaced; however, subjects who discontinue due to a DLT associated with the first infusion of pembrolizumab (ie, prior to any tabelecleucel infusion) will be replaced. Subjects who discontinue from Cohort 1 for any reason other than a DLT prior to completing the 21-day DLT assessment window will be replaced until the required number of evaluable subjects complete the 21-day DLT assessment window. Subjects will not be replaced in Cohort 2.

DLT definition: All toxicities will be graded based on the investigator's assessment using Common Terminology Criteria for Adverse Events (CTCAE) version 5, except for certain events described in the protocol which have a separate grading system. Specific toxicities (defined in the protocol) will be considered DLTs, if they are judged by the investigator to be possibly related or related to either investigational product tabelecleucel and/or pembrolizumab administration, excluding toxicities clearly not related to the investigational product, such as disease progression, environmental factors, unrelated trauma, etc.

The DLT window of observation will be during Cycle 1 of the Treatment Phase (ie, during the first 21-day cycle; adverse events [AEs] meeting the definition of a DLT but occurring after this period will not be considered DLTs).

Any subject experiencing a DLT will be withdrawn from treatment (both investigational products).

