Pembrolizumab: administered IV at a dose level of 200 mg for adults (\geq 18 years of age) or 2 mg/kg Q3W for children (12 to < 18 years of age). Pembrolizumab will be administered prior to the administration of tabelecleucel. Pembrolizumab will be administered on Day 1 of each 21-day treatment/consolidation cycle and on Day 1, Day 21 (\pm 2), Day 42 (\pm 2), and Day 63 (\pm 2) of each 84-day maintenance cycle.

Tabelecleucel: administered IV at doses of 1.2×10^6 cells/kg. Tabelecleucel will be administered 1 hour (\pm 10 minutes) after the completion of pembrolizumab. Tabelecleucel will be administered on Day 1, Day 8 (\pm 2), and Day 15 (\pm 2) of each 21-day treatment/consolidation cycle and on Day 1 of each 84-day maintenance cycle.

Dosing of both tabelecleucel and pembrolizumab, including dose modification and adjustment, will follow protocol guidance.

Duration of Treatment and Subject Participation

The duration of treatment is dependent on a subject's response to treatment and is estimated to be approximately 2 years for subjects with a response to treatment (CR, PR, or SD), which is a maximum of 4 treatment/consolidation cycles (21-day cycles with 3 infusions of tabelecleucel and 1 of pembrolizumab) and maintenance cycles (84-day cycles with 4 infusions of pembrolizumab and 1 of tabelecleucel) until up to a total of 35 pembrolizumab infusions (including for treatment, consolidation, and maintenance) have been given.

After treatment/consolidation and maintenance cycles, subjects will have an End-of-Treatment visit (30 days after the last dose of investigational product) and then enter Quarterly Follow-up for 12 months after the last dose of investigational product. Before receiving any treatment, subjects must undergo a tabelecleucel inventory check and screening, with screening up to 28 days prior to the first dose of investigational product.

Endpoints

The primary endpoints are:

- The incidence of DLTs in Cohort 1
- The MTD, or in the absence of an MTD the RP2D, of tabelecleucel when administered in combination with pembrolizumab
- The ORR of tabelecleucel in combination with pembrolizumab
- The characterization of the safety profile of tabelecleucel in combination with pembrolizumab in subjects with NPC

Secondary endpoints are:

- CR rate, DOR, PFS, and OS
- iRR (ie, iCR + iPR rate) and DOiR

Exploratory endpoints are:

CCI

CCI

Statistical Considerations

Analysis Population

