During the Treatment Phase, subjects will receive two 21-day treatment cycles of combination immunotherapy and then undergo a response assessment at the Observation Visit (refer to [Figure 1](#)). Based on the subject's response to the initial 2 cycles s/he may receive one additional consolidation cycle with the same tabelecleucel product or additional treatment cycles with tabelecleucel with the same or a different HLA restriction, if an appropriately matched product is available. Detailed descriptions are provided in [Section 15.2](#). At any time during the Treatment Phase if a subject has a confirmed progressive disease (cPD), it is at the investigator's discretion to continue treatment with tabelecleucel with a different HLA restriction (Switch Therapy), if available without pembrolizumab. A maximum of 4 treatment/consolidation cycles and 1 Switch Therapy, if available will be permitted.

During the Maintenance Phase, subjects will receive tabelecleucel on Day 1 and pembrolizumab on Day 1, Day 21, Day 42, and Day 63 of 84-day maintenance cycles, which will continue until disease progression, unacceptable toxicity, or a total of 35 pembrolizumab infusions (including for treatment, consolidation, and maintenance) have been given. After completing the End-of-Treatment (EOT) Visit 30 days after the last dose of investigational product, subjects will enter quarterly follow-up until 12 months after the last dose of investigational product or until disease progression. During this last phase, survival and disease status will be collected. The end-of-study is defined as the date of the last quarterly follow-up.

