4.6 Subject Withdrawal Criteria

A subject may withdraw either from (1) investigational product treatment only, in which case the subject will continue protocol defined follow-up assessments or (2) study participation, in which case investigational product and study assessments will be discontinued. Whenever possible, continue protocol-defined follow-up after the subject has discontinued investigational product treatment (refer to Section [6.7](#)).

Investigational product treatment may be discontinued for any of the following reasons:

- Occurrence of an AE that precludes further treatment, refer to Section [5.2.5](#)
- Achieves a sustained CR, refer to Section [5.2.4](#)
- Receives a prohibited treatment, such as use of a different investigational product or non-protocol anti-NPC therapy
- Decision (by subject or investigator) that continued investigational product treatment is not in the subject's best interest

Study participation may be discontinued for any of the following reasons:

- Withdrawal of consent by subject or subject's legally authorized representative
- Early closure of the study by the sponsor
- Subject is lost to follow-up

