5.2.4 Discontinuation of Treatment with Investigational Products after Complete Response

Discontinuation of treatment may be considered for subjects who have attained a confirmed CR that have been treated for at least 6 weeks with tabelecleucel and 24 weeks with pembrolizumab and had at least 2 treatments with pembrolizumab and 1 cycle tabelecleucel beyond the date when the initial CR was observed.

While subjects achieving a CR may discontinue treatment, they will not be considered to have discontinued the study unless consent is withdrawn. If study consent is not withdrawn the subject will complete an End-of-Treatment visit and enter in the Quarterly Follow-up Phase of the study.

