6.7 Early Withdrawal

For subjects who discontinue early from treatment, consolidation, or maintenance, the reason for discontinuation should be provided and the End-of-Treatment visit should be performed. The subject will be entered into Quarterly Follow-up, unless consent is withdrawn, for 12 months after the last dose of investigational product (tabelecleucel and/or pembrolizumab).

For a subject who discontinues early from quarterly follow-up, the reason for discontinuation should be provided and the last Quarterly Follow-up Visit will be considered the end-of-study for the subject.

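### Quarterly Follow-up, the only scheduled survival contact, ends at progression in some sections and runs a full 12 months in others

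*Protocol*

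**What the plan says.** Protocol 6.6 schedules visits every 90 ± 14 days for 12 months after the last dose, with this qualification: "tabelecleucel and/or pembrolizumab) or until disease progression. The last Quarterly Follow-up Visit will be considered the end-of-study for the subject". Section 3.1 has the same limit: "subjects will enter quarterly follow-up until 12 months after the last dose of investigational product or until disease progression". So do the Synopsis (Study Design), the procedural notes to 15.1, SAP 2.3, and the branches of 15.2.1 to 15.2.4 for subjects entering follow-up without current progression.

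Section 6.7, on subjects who stop treatment early, says otherwise: "The subject will be entered into Quarterly Follow-up, unless consent is withdrawn, for 12 months after the last dose of investigational product". The confirmed-progression branches of 15.2.1 to 15.2.4 also give 12 months with no progression stop. The Synopsis (Duration of Treatment) and Section 5.2.2 say only that subjects complete treatment "and then enter Quarterly Follow-up for 12 months after the last dose of investigational product" and do not mention progression.

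The list in Section 4.6 that opens "Study participation may be discontinued for any of the following reasons" names withdrawal of consent, early closure by the sponsor and loss to follow-up, but not progression. Section 5.2.4 says of subjects who stop treatment in complete response that "they will not be considered to have discontinued the study unless consent is withdrawn".

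In the schedule (15.1), the survival and disease status row is marked only under Quarterly Follow-up. The Synopsis adds: "During this last phase, survival and disease status will be collected through clinic visits or telephone contact". Section 3.1 leaves out the mode of contact, and 6.6 describes an assessment based on clinical and radiographic findings.

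**The concern.** Overall survival is a secondary endpoint (Protocol 3.2), to be summarized by Kaplan-Meier (9.2). If scheduled contact ends at progression, subjects are censored just as their risk of death rises. That censoring is informative and pushes the curve upward.

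Once contact stops, a death reaches the database only through safety reporting. Section 8.5.1 covers all deaths within 30 days of the last dose, and serious events to 90 days, or to 30 days if new therapy for the cancer starts sooner. After 30 days, 8.5 and note l to 15.1 otherwise collect only events judged at least possibly related.

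Sites reading 6.6 and 6.7, which are adjacent, could follow the same kind of subject for different lengths of time. The end-of-study date moves with the rule, because both sections tie it to the last quarterly visit. Section 6.7 does so even for a subject who leaves follow-up early: "For a subject who discontinues early from quarterly follow-up, the reason for discontinuation should be provided and the last Quarterly Follow-up Visit" is the end of study. SAP 7.1 reports end-of-study status as completed or not, without saying what completed means.

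**Working it through.** The plan gives no figure to reproduce here. The check is a comparison of the text, a visit count, and a sizing under stated assumptions.

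**1. The two rules side by side**

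| Ends at 12 months or progression | 12 months, no progression stop | 12 months, silent on progression |
|---|---|---|
| Synopsis (Study Design) | 6.7 | Synopsis (Duration of Treatment) |
| 3.1 | Confirmed-progression branches of 15.2.1–15.2.4 | 5.2.2 |
| 6.6 | | |
| 15.1, procedural notes | | |
| SAP 2.3 | | |
| Non-progression branches of 15.2.1–15.2.4 | | |

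**2. Visits under each rule**

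Visits at 90, 180, 270 and 360 days make 4 within 12 months. Progression during maintenance has no confirmed-progression branch: 15.2.1 to 15.2.3 end maintenance at progression and then start a follow-up phase that itself ends at progression.

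- Progresses in maintenance: 0 visits under 6.6 read literally, 4 under 6.7.
- Progresses at the first quarterly visit: 1 visit under 6.6, 4 under a rule with no progression stop.

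**3. Hand check of the worst case**

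Assume that all 12 subjects progress on treatment, that survival after the last dose is exponential with median m months, and that status is known only to day 30 (30/30.4375 = 0.986 months). Then

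unrecorded deaths = 12 × [(1 − 2^(−12/m)) − (1 − 2^(−0.986/m))].

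| m (months) | Deaths within 12 months | Of these, by day 30 | Unrecorded |
|---|---|---|---|
| 8 | 7.76 | 0.98 | about 6.8 |
| 10 | 6.78 | 0.79 | about 6.0 |
| 30 | 2.91 | 0.27 | about 2.6 |
| 60 | 1.55 | 0.14 | about 1.4 |

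These are ceilings for each m, because not every subject progresses on treatment.

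**4. Simulation**

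The event rates are assumptions. There were 400,000 subjects in each of 16 scenarios:

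- median progression-free survival 4 or 6 months, paired with median post-progression survival 8 or 10 months
- 10% or 20% of progression-free survival events fatal
- 1% or 3% per month stopping treatment without progression
- 0% or 20% of on-treatment progressors reaching response or stable disease on Switch Therapy
- treatment capped at 35 × 21 days, or 24.1 months

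True 12-month survival is 49–67%, and 6.5–8.4 deaths per 12 subjects fall within 12 months of the last dose.

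| Rule applied | Kaplan-Meier minus truth at 12 months (points) | Unrecorded deaths per 12 |
|---|---|---|
| Progression stop for everyone, status known to day 30 | 9.4–22.3 | 4.1–6.1 |
| Progression stop for everyone, status known to day 90 | 5.6–11.7 | 3.2–4.6 |
| Confirmed-progression branches for all on-treatment progression | 0–1.6 | 0–1.4 |
| 12 months for everyone | 0 | 0 |

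In the third row the upper bias of 1.6 arises when 6.6 is still applied to subjects who stop treatment early without progression. If 6.7 covers them, the bias is 0–0.8.

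**5. Sensitivity to survival**

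Protocol 1.3 reports 11 of 14 tabelecleucel-treated subjects with this cancer alive at a median of 18.1 months (range 3.0–48.4) after starting. With assumed post-progression medians of 30–60 months (18-month survival 61–81%), the progression stop for everyone leaves about 1.0–2.3 deaths per 12 unrecorded.

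**The case against.** The best defense is that the specific text already settles most cases. Section 6.7 covers anyone who discontinues treatment, consolidation or maintenance early, 4.6 asks for follow-up to continue whenever possible, and the confirmed-progression branches give 12 months. On that reading only subjects who enter follow-up without progression stop at progression, and little is lost. This has force, and it is why the worst-case figures should not lead. It does not remove the conflict. Section 6.6, 3.1, the Synopsis and SAP 2.3 apply the progression stop without exception, and nothing says that 6.7 overrides them. The reading would also follow survival after progression on treatment but not after progression in follow-up, with no reason given.

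A second objection is that the sizing rests on assumed survival. That is correct. The 14 subjects in Protocol 1.3 are few, come from another study and had partly short follow-up, but they make lower counts plausible.

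A reader might also infer more than the documents support:

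- **That reported survival will be biased by up to 22 points.** The SAP plans no survival curve (SAP 1, 3.2, 6.2), and the figure sets aside 6.7 and 4.6.
- **That the Synopsis (Duration of Treatment) and 5.2.2 require follow-up past progression.** They are silent on it.
- **That counts of subsequent anti-cancer therapy would be cut short.** Neither rule schedules such an item in follow-up, and SAP 11.3 reports it only if data are available.
- **That response rates are affected.** SAP 8.1.1 excludes follow-up assessments.

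**Conclusion.** The stopping rule is wrong as written, and the inconsistency is minor. No passage reconciles 6.6 with 6.7, and for subjects who progress in maintenance the difference is 0 visits against about 4.

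The size depends on which text a site follows. If 6.7 and the confirmed-progression branches govern, the effect is 0–1.6 points on 12-month Kaplan-Meier survival and 0–1.4 unrecorded deaths per 12 subjects, under the assumed rates. A progression stop for everyone is the worst case: about 6–22 points and 3.2–6.1 deaths, falling to about 1–2 deaths if survival is longer.

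The study was terminated with 12 subjects and survival will only be listed and plotted. The remaining effect is therefore on the survival listing and swimmer plot (SAP 3.2), the death summary and listing (SAP 11.1) and end-of-study status (SAP 7.1). That the rule changes who counts as completed is an inference, because the SAP does not define the term. The counts assume that termination did not itself cut follow-up; sponsor closure (Protocol 4.6) may have ended contact under either rule.

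**What to change.** **Protocol.** Reconcile the Synopsis (Study Design), 3.1, 6.6, the notes to 15.1, SAP 2.3 and the branches of 15.2 with 6.7, so that survival status is collected for all subjects through 12 months after the last dose regardless of progression. Carry the Synopsis allowance for telephone contact into 3.1 and 6.6. Define end of study as the last survival contact. Leave the imaging rules as they are, including the iRECIST provision in 7.1.2.3; the change concerns survival contact only.

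**SAP, for the 12 enrolled subjects.** Add the last-known-alive date and the reason follow-up ended, which 6.7 already collects, to the survival listing and swimmer plot. State which follow-up rule defines completed in the disposition table (SAP 7.1).

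**Cost.** Up to four brief contacts per progressed subject in a continuing study; now, two listing columns and one SAP sentence. The 12-month limit itself would remain, leaving 1.2–3.1 points of upward bias in any 24-month survival estimate under the same assumptions.
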